4. Must have documentation of no evidence of disease progression of the tumor during or after completion of first line systemic anti-cancer therapy as determined by the investigator using RECIST v1.1 guidelines. Subjects who have a tumor response of SD with evidence of \geq 15% to 20% increase in tumor burden will be submitted for Central Review to adjudicate the investigator's assessment of tumor response prior to randomization. Subjects with NED are eligible.
 5. Have an Eastern Cooperative Oncology Group (ECOG) performance status of 0 or 1.
 6. Age \geq 12 years.
 7. Have a life expectancy of at least 6 months, as determined by the investigator.
 8. If a female of child-bearing potential (FCBP), willing to undergo pregnancy testing and agree to use at least 1 highly-effective contraceptive method, such methods include combined estrogen and progesterone-containing hormonal contraception associated with inhibition of ovulation (oral, intravaginal, transdermal) or progesterone only hormonal contraception associated with inhibition of ovulation (oral, injectable, implantable), intrauterine device (IUD), intrauterine hormone-releasing system (IUS), bilateral tubal occlusion, vasectomized partner or true sexual abstinence (when this is in line with the preferred and usual lifestyle of the subject, refraining from heterosexual intercourse during the entire period of risk associated with study treatments) during the dosing period and for 1 month (which is the duration of a menstruation cycle) after administration of the last dose of CMB305. More stringent contraception criteria should be followed if requested by local regulatory authorities.
 9. If male and sexually active with a FCBP, must be surgically sterile (i.e., vasectomy) or agree to use highly-effective contraception, such as latex condom, during the dosing period and for 3 months (which is the duration of a sperm cycle) after administration of the last dose of CMB305. More stringent contraception criteria should be followed if requested by local regulatory authorities.
 10. Have recovered from the toxic effects (except alopecia) to grade 2 or better from systemic anti-cancer therapy according the National Cancer Institute-Common Terminology Criteria for Adverse Events (NCI-CTCAE) Version 4.03 (or newer).

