6.4.7.5 Definitions of Adverse Event

Adverse Event (AE)—Any untoward medical occurrence in a subject or clinical investigation subject administered a pharmaceutical product, medical treatment, or procedure, and which does not necessarily have to have a causal relationship with this regimen. An AE can therefore be any unfavorable and unintended sign (including an abnormal laboratory finding, for example), symptom, or disease temporally associated with the use of a medicinal product, medical

treatment, or procedure whether or not considered possibly, probably, or definitely related to the medicinal product. Progression of cancer is not considered an AE unless it is considered to be drug-related by the investigator.

Treatment-Emergent Adverse Event (TEAE)—Any AE that occurs, or an existing condition that worsens in severity, after administration of the first dose of the study drug.

Medical Event of Interest (MEOI)—Selected non-serious AEs are classified as MEOIs. The following treatment-emergent immune-mediated event is an MEOI for CMB305:

- Pneumonitis

As NY-ESO-1 is only detected in certain testicular cells in healthy individuals ([Gnjatic 2006](#)), the following male genitourinary-related events are MEOIs for CMB305:

- Prostatic pain
- Groin pain
- Testicular pain
- Epididymo-orchitis

MEOIs for this study include the following:

- An overdose of the sponsor's investigational product that is not associated with clinical symptoms or abnormal laboratory results
- Results from protocol-specified or unscheduled laboratory results showing simultaneous:
 - Increased ALT and/or AST $\geq 3 \times$ ULN,
 - Increased serum total bilirubin $\geq 2 \times$ ULN, without initial findings of cholestasis (elevated serum alkaline phosphatase) and
 - No other reason can be found to explain the combination of increased aminotransferase enzymes and total bilirubin, such as viral hepatitis A, B, or C; preexisting or acute liver disease; or another drug capable of causing the observed injury.

Note: These criteria are based upon available regulatory guidance documents.

The purpose of these criteria is to specify a threshold of abnormal hepatic test results that may require an additional evaluation for an underlying etiology. The site guidance for assessment and follow-up of these criteria can be found in the Investigator Trial File Binder (or equivalent).

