7.8 Safety Analysis

Safety will be assessed primarily based on reported AEs. A TEAE is an AE with an onset on or after the initiation of study treatment, or a pre-existing condition that worsens after initiation of study treatment (i.e., increase in severity). Medical events of interest, immune-mediated events, and AEs that occur more than 30 days after the last dose, and that are deemed as related to the study drug, will be included as TEAEs. TEAEs occurring from the time of the first dose through 30 days after the last dose of the study drug and medical events of interest, immune-mediated events and related AEs will be summarized. All AEs will be coded using the Medical Dictionary for Regulatory Affairs® (MedDRA v20.0 or newer). TEAEs will be tabulated by system organ class, preferred term, by treatment, and will be further categorized by NCI-CTCAE (v4.03 or newer) grade, and by relationship to the study drug. Clinically significant laboratory abnormalities, as measured by either the local or central laboratory, will be reported as AEs. The incidence for each AE will be provided as the total number of subjects that experience the AE, as well as the percentage of the population that this represents. If an AE is reported more than once during treatment for a given subject, the worst grade of severity and the most conservative relationship will be presented in the summary tables.

AEs will also be listed for individual subjects, along with information regarding onset, duration, grade, relationship to the study drug, and outcome. AEs that lead to withdrawal from the study treatment will be listed and summarized. Tabulations and listings of SAEs and deaths also will be generated.

Treatment exposure will be provided by treatment arm. The number of CMB305 or placebo injections, duration of exposure, and number of subjects with dose reductions/interruptions will be summarized by treatment arm based on the Safety set.

Laboratory values measured by the central laboratory will be used in the analysis of laboratory toxicities and will be defined based on universal normal ranges and NCI-CTCAE, Version 4.03 or newer. The number and percentage of subjects will be summarized by grade using the most severe grade by treatment arm. Clinically significant changes in laboratory values will be summarized by treatment arm. Laboratory values will be listed, with grade 3 or 4 values flagged.

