## 6.3 Safety Set

The Safety set consists of all subjects taking any amount of study drug. The safety set is the primary set for safety analyses including AEs and clinical laboratory data. Study treatment exposure also will be summarized using the safety set.

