## 8.3 Safety Analyses

All analyses for the safety evaluation variables will be performed on safety set by treatment arm and overall.

Baseline is defined as the last non-missing value prior to the first dose date on day 1, unless otherwise noted.

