### 8.3.1 Adverse Events

The verbatim terms used in the eCRF by investigators to identify adverse events will be coded to a system organ class (SOC) and a preferred term (PT) using the current Medical Dictionary for Regulatory Activities (MedDRA) version 21.0 or higher. The severity of adverse events is assessed in National Cancer Institute (NCI) common toxicity criteria for adverse events (CTCAE) Version 4.03 or higher. Only TEAEs occurring from the time of the first dose through 30 days after the last dose of the study drug and medical events of interest, immune-mediated events and related AEs will be summarized, while all AEs captured in eCRF will be listed in data listings.

TEAE will be summarized by system SOC and PT, by severity, by relationship to study treatment, and by action taken. Tables will be sorted by frequency in incidence (the highest to lowest incidence in total column).

The following TEAEs will be tabulated and organized as follows:

- Overall Summary of Treatment Emergent Adverse Events
- TEAEs by system organ class and preferred term
- TEAEs by system organ class, preferred term and worst NCI CTCAE grade
- Severe TEAEs (Grade 3 or higher) by system organ class and preferred term
- SAEs by system organ class and preferred term and worst NCI CTCAE grade
- Related TEAEs by system organ class and preferred term
- Related SAEs by system organ class and preferred term
- Related TEAEs by system organ class, preferred term and worst NCI CTCAE grade
- Related SAEs by system organ class and preferred term and worst NCI CTCAE grade
- TEAEs leading to treatment discontinuation by system organ class and preferred term
- Related TEAEs leading to treatment discontinuation by system organ class and preferred term
- TEAEs classified as Medical Event of Interest (MEOI) by system organ class and preferred term
- TEAEs resulting in death by system organ class and preferred term

TEAEs will be summarized by presenting the number and percentage of subjects having at least one TEAE in each system organ class and preferred term. A subject with multiple occurrences of the same TEAE will be counted only once in the AE category.

Separate TEAE summaries will be presented by system organ class, preferred term, and maximum CTCAE (4.03 or higher) grade. A subject with multiple CTCAE grades for the same TEAE will be summarized under the maximum CTCAE grade recorded for the event.

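### Male-only events of interest are shown as a percentage of all treated subjects, so the shown rate understates the risk to a treated man by the female share

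*SAP*

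**What the plan says.** Protocol 6.4.7.5 gives the reason for the category, "As NY-ESO-1 is only detected in certain testicular cells in healthy individuals", and then states that "the following male genitourinary-related events are MEOIs for CMB305". It lists prostatic pain, groin pain, testicular pain and epididymo-orchitis. The same section describes MEOIs as selected non-serious events.

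The denominator comes from general rules:

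- SAP 8.3: "All analyses for the safety evaluation variables will be performed on safety set by treatment arm and overall".
- SAP 6.3: "The Safety set consists of all subjects taking any amount of study drug".
- SAP 8.3.1: treatment-emergent events are summarized by "presenting the number and percentage of subjects having at least one TEAE in each system organ class and preferred term". The list of tables includes "TEAEs classified as Medical Event of Interest (MEOI) by system organ class and preferred term".
- Protocol 7.8: each event is given as a count of subjects, "as well as the percentage of the population that this represents".

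Women are eligible. Protocol 4.2 has a criterion that begins "If a female of child-bearing potential (FCBP), willing to undergo pregnancy testing". Sex is summarized as a baseline characteristic on the ITT set (SAP 8.1.3) and is not a stratification factor (SAP 3.3.1). Neither document provides for an adverse event or MEOI summary by sex.

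**The concern.** The protocol singles out these terms on a biological argument about men: the vaccine's target antigen is present in normal testicular cells. The question for a reader is therefore how often the events occur in treated men. The planned percentage counts women, who cannot have three of the four events, as event-free. It answers a different question, and its value moves with the sex mix of the trial.

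Because MEOIs are by definition selected non-serious events, the serious-event tables would not show them. The MEOI table is the one planned summary that isolates them, so the scale of its percentage matters. What is at stake is the reported absolute risk of a harm that the protocol names. No efficacy conclusion depends on it.

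**Working it through.** **Inputs.** Planned arm size is 124 (SAP section 4), and all are taken as treated. The male share m is not in the documents, so it is an assumption, shown over 40% to 60%. The documents give no rate for these events, so there is no stated figure to reproduce.

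**Step 1: size of the understatement.** For an event that only men can have,

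shown percentage = (risk in men) × m,

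so the relative understatement is 1 − m, the female share. This step needs no assumption about the risk. The risk in men is 1/m times the shown figure: 2.5, 2.0 or 1.67 times at m = 40%, 50% or 60%.

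**Step 2: an example.** Three events in an arm of 124 show as 3/124 = 2.4%. On the male denominator:

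| Assumed male share | Men in arm (124 × m) | 3 events as % of men | Understatement |
|---|---|---|---|
| 40% | about 50 | 6.0% | 60% |
| 50% | 62 | 4.8% | 50% |
| 60% | about 74 | 4.0% | 40% |

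**Step 3: no events.** The exact one-sided 95% upper bound is 1 − 0.05^(1/n). With n = 124 it is 2.4%. With n = 62 (50% male) it is 4.7%. Over the range 40% to 60% male (n of about 50 to 74) it is 5.8% to 4.0%. At 50% male, the all-subject denominator makes a clean result look about twice as reassuring as it is.

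**Step 4: comparison between arms.** If both arms have the same male share, m cancels from the ratio of rates. Without stratification by sex, the difference in number of men has SD √(2 × 124 × m(1 − m)), which is √62 = 7.9 at m = 50%. A split of 70 v 54 men is about 2 SD and makes equal risks look 70/54 = 1.30 apart.

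To put that in proportion, take an illustrative 10% risk in men, which has no source in the documents. Expected events are 7.0 v 5.4, a gap of 1.6. Binomial variation in the difference has SD √(0.1 × 0.9 × 124) = 3.3 events. An unusual imbalance therefore shifts the comparison by about half an SD of ordinary sampling noise.

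**The case against.** **The denominator is inferred.** SAP 8.3.1 does not write out the denominator of the MEOI table, and the table shells are in separate files (SAP section 11), which could carry a male n. This cannot be excluded. But the SAP's general rules lead to all treated subjects, nothing in the text provides an exception, and a rule for a risk that the protocol names belongs in the plan itself.

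**Nothing is lost.** Counts stand beside the percentages, events are listed by subject, and sex is tabulated by arm. A reader could closely approximate the rate in men, although sex is tabulated on the ITT set and the events on the Safety set. This stands, and it limits the consequence. The reported figure is still on the wrong scale, and the reader would have to rebuild it.

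**Masking or mimicking a treatment effect.** A reader might infer that chance sex imbalance could hide or create a difference between arms. The documents do not support that as a main concern. The adverse event tables are descriptive, with no test between arms, and Step 4 shows the distortion to be small against sampling noise.

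**Mixed denominators.** Putting male denominators on single preferred-term rows of the general tables could let a preferred-term percentage exceed that of its system organ class. Limiting groin pain to men would leave groin pain in women unassigned. Both objections are right and shape the fix.

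**The rationale is narrower than the list.** The antigen argument concerns testicular cells, while prostatic and groin pain are not testicular and groin pain is not male-only. That is fair. It does not change the denominator problem for the three terms that only males can have.

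**Conclusion.** The point holds as a reporting matter. Under the SAP's stated rules, the percentage for prostatic pain, testicular pain and epididymo-orchitis is too low, as a risk to a treated man, by exactly the female share. That is 40% to 60% in relative terms if 40% to 60% of subjects are male. The range is an assumption. The direction is certain once any women are treated.

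The conclusion rests on reading SAP 6.3, 8.3 and 8.3.1 and protocol 7.8 together, and would lapse if the unseen table shells already specify a male n. It does not extend to a claim that treatment differences would be masked or mimicked, or that harm would be concealed, since counts and listings are planned. It is worth correcting because the change is small and the harm is one that the protocol itself singled out.

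**What to change.** In SAP 8.3.1, add a separate MEOI summary, or a footnoted row block, with these rules:

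- Prostatic pain, testicular pain and epididymo-orchitis use the number of male subjects in that arm's Safety set as denominator, with that n displayed.
- Groin pain is reported for males on the male denominator, and separately for all subjects.
- The general tables by system organ class and preferred term stay on the all-subject denominator, so that denominators are not mixed within a table.
- The preferred terms counted under each MEOI term are listed.

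Protocol 8.17 has MEOIs supplied to the data monitoring committee as its charter specifies, so ask that the charter adopt the same convention for those tables.

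The cost is one extra table or row block and the programming for it. Sex is already collected. No dose, stopping rule or other clinical management rule is affected.

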### **8.3.2 Clinical Laboratory Evaluations**

All laboratory values will be converted to SI units and classified as normal, low, or high based on the normal ranges of local/central lab. All gradable laboratory parameters will be graded using the NCI CTCAE v4.03 or higher. The worst post-baseline toxicity grade will be summarized for hematologic, chemistry and coagulation parameters for all gradable laboratory parameters, otherwise, the worst abnormal will be presented instead.

Standard descriptive statistics will be presented for clinical laboratory tests, at baseline, each scheduled visit and change from baseline on safety set by each treatment arm and overall.

If lab results contain symbols like “<”, “>”, “>=” or “<=”, extract the numeric value as the limit, Example: if result is “>0.1”, “0.1” will be used for analysis.

Subject listings of laboratory test results for hematology, chemistry, urinalysis, coagulation and other laboratory tests will be provided separately. Values with CTC grade as 3 or above will be flagged in the listings.

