f Obtain and review images (CT or MRI) collected at the standard-of-care time point for the first evaluation of response to first-line systemic anti-cancer therapy. The subject's response to first-line systemic anti-cancer therapy will be assessed by the investigator using RECIST v1.1 and documented in the eCRF.

g Tumor imaging (CT or MRI) will be performed after completion of the planned 4-cycles to 8-cycles of first-line systemic anti-cancer therapy for the evaluation of response at baseline, as assessed by the investigator using RECIST v1.1. The images collected at this time point will serve as the baseline assessment for the efficacy evaluations. These images must be collected within 28 days after the date of last dose of first-line systemic anti-cancer therapy.

h Results from the central laboratory will be used to determine eligibility and for the safety analysis. Laboratory tests performed by the central laboratory will include: chemistry with liver function tests, lactate dehydrogenase, alkaline phosphatase, albumin, hematology with complete blood count with differential, HIV, HepB, and HepC. Coagulation samples will be drawn only at Screening and shipped to the central laboratory (prothrombin time, partial thromboplastin time, and international normalized ratio) for analysis. Urinalysis will be conducted at the central laboratory. All laboratory assessments to be performed are listed in protocol Table 4.

i The peripheral blood on all subjects must be collected Day -28 to Day -7 during Screening and will be used for plasma ELISA testing; results of the assessment will be used for stratification and randomization.

j For circulating tumor genomics, please see lab manual.

k For FCBP, serum pregnancy testing will be performed during Screening.

l Vital sign measurements will include body temperature, heart rate, respiratory rate, and resting systolic and diastolic blood pressure.

m At Screening, the physical examination should include an evaluation of organ systems, including, but not limited to, head and neck; chest and lungs; cardiac; gastrointestinal; neurologic; endocrine; and musculoskeletal and integument. Other organ systems should be evaluated as directed by medical history or current symptoms. Measurements of body weight and height will be obtained.

Table 2 Schedule of Events for the Treatment Period through Long-term Follow-up Period

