## **5.2 Safety Endpoints**

### **5.2.1 Adverse Events**

A treatment-emergent adverse event (TEAE) is defined as any AE that newly appeared or worsened in severity following initiation of the study treatment administration until 30 days after last dose of the study treatment. In addition, all study treatment related AEs are treated as TEAE.

Medical Event of Interest (MEOI) is defined as selected non-serious AEs are classified as MEOIs, refer to protocol section 6.4.7.5 for more details.

Immune-mediated event --

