### **8.3.8 Analysis of Other Safety Variables**

Analyses for other safety variables will be performed based on the nature of the parameters and assessment schedule as needed.

A shift table for ECOG comparing the worst post baseline to baseline will be presented by treatment arm and overall.

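### The laboratory grade table in SAP 8.3.2 takes no account of baseline grade, so residual Grade 1-2 abnormalities from chemotherapy count as on-study toxicity in both arms and dilute low-grade differences

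*SAP*

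**What the plan says.** SAP 8.3.2 sets out one graded laboratory summary: "The worst post-baseline toxicity grade will be summarized for hematologic, chemistry and coagulation parameters for all gradable laboratory parameters". Protocol 7.8 is equivalent: "The number and percentage of subjects will be summarized by grade using the most severe grade by treatment arm". Neither mentions baseline grade, and neither document states a laboratory shift table or a count of treatment-emergent laboratory grades.

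Baseline is not ignored altogether. SAP 8.3.2 also says "Standard descriptive statistics will be presented for clinical laboratory tests, at baseline, each scheduled visit and change from baseline on safety set", and protocol 7.8 adds "Clinically significant changes in laboratory values will be summarized by treatment arm". The protocol gives no criterion for that second summary, and SAP 8.3.2 does not repeat it.

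On entry, protocol 4.2 (criterion 10) requires that subjects "Have recovered from the toxic effects (except alopecia) to grade 2 or better from systemic anti-cancer therapy". Protocol 4.3 excludes cancer therapy within three weeks before first dosing and a last dose more than 28 days before Day 1, subject to the extension in protocol 3.3.

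Elsewhere the SAP does refer to baseline. Section 5.2.1 defines a treatment-emergent event as "any AE that newly appeared or worsened in severity following initiation of the study treatment administration". Section 8.3.8 says "A shift table for ECOG comparing the worst post baseline to baseline will be presented by treatment arm and overall". Section 8.3.4 gives QTc categories for change from baseline.

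On coagulation, footnote h to SAP Table 1 says "Coagulation samples will be drawn only at Screening and shipped to the central laboratory".

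**The concern.** This population comes straight from first-line chemotherapy, so some subjects will have abnormal haematology or chemistry on Day 1. A subject at Grade 2 before dosing and still at Grade 2 on Day 22 has not worsened, yet the planned table records a post-baseline Grade 2. A subject recovering from Grade 2 to Grade 1 is recorded as Grade 1. The table mixes residual chemotherapy effect with anything that CMB305 does.

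Two things are at stake. The absolute low-grade laboratory rates reported for CMB305 would be too high, and so would those for placebo. A real difference between arms in new Grade 1-2 abnormalities would also look smaller than it is. In addition, the table includes post-baseline coagulation grades for which no sample is scheduled.

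**Working it through.** The documents give no figure to reproduce here. The check has three parts.

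**1. Timing.** Protocol 4.3 places the last chemotherapy dose 21 to 28 days before Day 1, unless extended. In SAP Table 2, chemistry and haematology are drawn on Days 1, 22, 50, 64 and 92, before dosing. SAP 8.3 defines baseline as the last value before the first dose, so the Day 1 sample normally supplies it. The first scheduled post-baseline sample is Day 22, 21 days later. That is 21 + 21 = 42 to 28 + 21 = 49 days after chemotherapy, give or take the 3-day window. Some recovery by then is plausible, so persistence is varied below.

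**2. Dilution.** The following are assumptions; the documents give none of these values:
- p0 and p1: new-onset risk of Grade 2 or higher on placebo and CMB305
- b: share of subjects at Grade 2 at baseline, equal in expectation by randomisation
- r: share of those still at Grade 2 or higher at some post-baseline draw
- n = 124 per arm (SAP 4), taken as the approximate Safety set size

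Subjects who recover are given the new-onset risk. The planned table then shows, per arm,

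P = b[r + (1 − r)p] + (1 − b)p = br + (1 − br)p,

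so the difference between arms shrinks from p1 − p0 to (1 − br)(p1 − p0).

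With p0 = 5%, p1 = 15%, b = 20%:
- r = 100%: 0.20 + 0.80 × 0.05 = 24.0%, and 0.20 + 0.80 × 0.15 = 32.0%. The ratio is 1.33 instead of 3.0.
- r = 50%: 0.10 + 0.90 × 0.05 = 14.5%, and 0.10 + 0.90 × 0.15 = 23.5%. The ratio is 1.62.

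Visibility is expressed as the power of a two-sided 0.05 normal comparison of two proportions. The baseline-referenced comparator uses only subjects below Grade 2 at baseline, that is n(1 − b) per arm (124 × 0.8 ≈ 99), with the undiluted p0 and p1.

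| p0 v p1 | b | r | Planned table | Power, planned | Power, baseline-referenced |
|---|---|---|---|---|---|
| 5% v 15% | 10% | 100% | 14.5% v 23.5% | 0.44 | 0.70 |
| 5% v 15% | 20% | 100% | 24.0% v 32.0% | 0.29 | 0.65 |
| 5% v 15% | 20% | 50% | 14.5% v 23.5% | 0.44 | 0.65 |
| 5% v 15% | 40% | 100% | 43.0% v 49.0% | 0.16 | 0.53 |
| 5% v 10% | 20% | 100% | 24.0% v 28.0% | 0.11 | 0.27 |
| 10% v 25% | 20% | 100% | 28.0% v 40.0% | 0.51 | 0.80 |

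For the first pair of risks with b = 0, the two tables coincide, with power 0.75. That value is not a fair comparator when b > 0, because subjects already at Grade 2 cannot newly reach it.

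**3. Higher grades.** If entry is capped at Grade 2, then b = 0 for Grade 3 or higher and the planned count equals the treatment-emergent count. The exception is a subject who worsens between the eligibility sample and Day 1. The organ-function limits in protocol 4.3 further restrict which parameters can be abnormal at entry. The documents do not translate them into CTCAE grades, so they are not used here.

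**The case against.** The strongest reply is that this is a randomised, placebo-controlled trial with the same entry rules and draw schedule in both arms. Placebo shows the background rate, and carry-over is balanced in expectation. That is correct. A reader might infer that the table hides a CMB305 safety signal, but the documents do not support this. The effect is dilution of low-grade differences in one descriptive table.

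The protocol reports results by grade, so a later Grade 3 or 4 appears as such, and SAP 8.3.2 flags those values in listings. This also stands, and it confines the point to Grades 1-2.

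Other outputs refer to baseline, and they help only in part:
- Change-from-baseline statistics are group summaries and do not show which subjects changed grade.
- A laboratory abnormality becomes an adverse event only if it leads to action on study drug, requires intervention, or is judged clinically significant by the investigator (protocol 6.4.7.8). An asymptomatic shift from Grade 1 to Grade 2 can be missed.
- Simultaneous transaminase and bilirubin elevation is a medical event of interest with its own table. That covers one serious pattern, not grade shifts generally.
- The protocol's summary of clinically significant changes has no criterion and is absent from SAP 8.3.2, while SAP 9 lets the SAP prevail where the two differ.

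On coagulation, a reader might infer that the row must be empty and would be read as no toxicity. The documents do not go that far. Local results may be collected for subjects with adverse events (protocol 6.4.3.1), so unscheduled values could exist. What stands is that none is scheduled.

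Finally, table shells are held in separate mock-up files (SAP 11) that are not available here, and a shift shell may exist. The SAP text should specify it in either case.

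**Conclusion.** The point holds as one of safety presentation. The stated laboratory grade table is not referenced to baseline, in subjects who may enter at Grade 2. It overstates absolute Grade 1-2 rates in both arms and dilutes, without biasing, the Grade 1-2 comparison. Primary endpoints and data collection are unaffected.

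Under the 5% v 15% assumption with 20% abnormal at baseline, power is about 0.29 to 0.44 for the planned table, depending on persistence, against about 0.65 for the baseline-referenced one. These values rest on assumed risks, prevalence and persistence. Because no laboratory test is planned, they measure how visible a difference would be and not the operating characteristics of a planned analysis. The direction does not depend on the particular values: whenever some baseline abnormality persists, the planned table shrinks the difference.

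**What to change.** In SAP 8.3.2, add for each gradable parameter, by arm:
- a shift table of baseline grade by worst post-baseline grade, using the baseline already defined in SAP 8.3;
- the number and percentage of subjects with a treatment-emergent increase, reported as at least one grade above baseline and as an increase to Grade 3 or higher.

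This brings laboratory grades into line with how the SAP already treats adverse events and ECOG. The worst-grade summary can stay alongside.

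Remove coagulation from the post-baseline grade summary, report it at Screening, and list any unscheduled local values.

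The cost is SAP wording and one extra standard table shell. The data are already collected, and no change to eligibility or sampling is needed.
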